#### 6.10.1. Sensitivity Analysis

The subgroups of subjects originally randomized to HMTM 16 mg/day and 8 mg/day will be analyzed separately, as described in Section 6.10.

#### 6.11. Exploratory Efficacy Analysis

ADCS-ADL23, and the MRI parameters (whole brain and temporoparietal lobe) will be analyzed analogously to the ADAS-cog11, see Section 6.10, to directionally support a disease modifying argument. Subgroup analyses might be done in a post-hoc analysis.

Sponsor:	TauRx Therapeutics Ltd.		
Protocol:	TRx-237-039		
Document Version No.:	3.0	Document Date:	07-JUN-2023

#### 6.11.1. ADCS-ADL23

Compared to ADAS-cog11, with a similar range of values and estimated treatment effect of  $5.0 \pm 1.6$  (mean  $\pm$  standard error) units from a pooled analysis of the studies TRx-237-005 / TRx-237-015, the non-inferiority margin will be set to -2.

The null and alternative hypothesis can be written as:

$H_0: \mu_{\text{early}} - \mu_{\text{late}} \leq -2$ ; versus

$H_1: \mu_{\text{early}} - \mu_{\text{late}} > -2$ .

Regarding the SAS code, the *UPPER* option will be used in the *LSMESTIMATE* statement.

#### 6.11.2. MRI

For the MRI parameters the non-inferiority margin will be set to -13,000 ( $\text{mm}^3 = \mu\text{L}$ ) for whole brain volume and -800 ( $\text{mm}^3 = \mu\text{L}$ ) for the temporoparietal lobe volume.

### 6.12. Post Hoc Efficacy Analysis

The following efficacy analysis have been added after partial unblinding of study team members. The partial unblinding was done to be able to perform the analysis of the double-blind treatment phase.

To complete the efficacy analysis (see Sections 6.10 and 6.11), based on the ITTv5-OL population (see Section 3.1.2), summary statistics of the absolute values and their change from Baseline-OL of the scales (ADAS-cog11, ADAS-cog13, ADCS-ADL23, Composite Scale, and COVID-19 Composite Scale), MRI parameters (whole brain, temporoparietal lobe, putamen, nucleus accumbens, nucleus basalis, hyperintensities total volume, and hypointensities total lesion volume) will be tabulated by visit (including Baseline-OL, Week 78, and Week 104) and HMTM treatment group as described above. MMSE and CDR-SOB will be tabulated by visit (including Baseline-OL and Week 104) and HMTM treatment group. Upscaling rules will be applied (see Section 4.5.1) and analyses are performed on these upscaled values. The summary statistics of ADAS-cog11, ADCS-ADL23, and the MRI parameters whole brain volume and temporoparietal lobe volume will be presented based on the PPv5-OL population as well.

Also, summary statistics and treatment differences (with 95% confidence intervals) based on the least squares means (LSM) from the corresponding MMRM models (see Sections 6.10 and 6.11) will be presented for the study visits Baseline-OL, Week 78, and Week 104.

Based on the ITTv5-OL population, for ADAS-cog13, ADAS-cog11, ADCS-ADL23, and the two MRI parameters whole brain volume and temporoparietal lobe volume, line graphs (showing the LSM and standard error) will be generated, presenting the MTC 8 mg/week group and the HMTM 16 mg group (along with their corresponding tables, presenting the LSM and treatment contrast for each visit). The LSM are based on a restricted maximum likelihood-based MMRM including a nominal visit variable, the

Sponsor:	TauRx Therapeutics Ltd.		
Protocol:	TRx-237-039		
Document Version No.:	3.0	Document Date:	07-JUN-2023

treatment indicator and the interaction term between treatment and visit, the randomization stratification variables (see Section 2.6) as fixed factors, and the respective efficacy Baseline/Baseline-OL value as covariate; with an unstructured covariance matrix and the Kenward and Roger method of calculating the denominator degrees of freedom for the tests of fixed effects. One version of the line graph will include/present the visits from Baseline to Week 104, including Baseline as the covariate in the model, and a second version will include/present the visits from Baseline-OL to Week 104, including Baseline-OL as the covariate in the model. This will be repeated for the verified AD diagnosis subgroups MCI-AD and probable AD.

Based on the ITTv5-OL population, the following pairwise correlations will be analyzed by means of scatter plots with symbolized treatment groups, which include both the parametric Pearson correlation coefficient and the non-parametric Spearman's rank correlation coefficient and their corresponding p-values for each treatment group, along with the regression lines:

- (Changes from Baseline): MRI whole brain volume at Week 52 vs. ADAS-cog11 at Week 104
- (Changes from Baseline): MRI whole brain volume at Week 52 vs. ADCS-ADL23 at Week 104
- (Changes from Baseline): MRI whole brain volume at Week 52 vs. CDR-SOB at Week 104
- (Changes from Baseline): MRI whole brain volume at Week 52 vs. MMSE at Week 104

Based on the ITTv5 population, for ADAS-cog13, ADAS-cog11, ADCS-ADL23, and the two MRI parameters whole brain volume and temporoparietal lobe volume, the observed change from Baseline at Weeks 26, 52, 78, and 104 will be analyzed with a paired t-test, separately for the subjects originally randomized to HMTM 16 mg/day and subjects originally randomized to MTC 8 mg/week. Two-sample t-test comparisons between the treatment groups for the respective endpoints and each of the Weeks 26, 52, 78, and 104 will be presented as well. This will be repeated for the verified AD diagnosis subgroups MCI-AD and probable AD.

Based on the ITTv5 population, for the ADAS-cog11, the change from Baseline at Week 52 will be analyzed with the paired t-test, separately for the subjects originally randomized to HMTM 16 mg/day and subjects originally randomized to MTC 8 mg/week. The change from Baseline-OL to Week 104 based on the ITTv5-OL population will be analyzed the same way. This will be repeated for the verified AD diagnosis subgroups MCI-AD and probable AD.

Sample SAS code (will be fully validated at the analysis stage):

```
PROC TTEST DATA=dataset ALPHA=.05;  
  BY treatment;  
  VAR scorediff;  
  RUN;
```

Sponsor:	TauRx Therapeutics Ltd.		
Protocol:	TRx-237-039		
Document Version No.:	3.0	Document Date:	07-JUN-2023

### 6.13. Safety Analysis

Safety analyses will be conducted using the Safety-OL population (see Section 3.1.2), presenting the data from the open-label treatment phase, whereas the last non-missing value prior to the first dose of the open-label treatment phase study drug will serve as the Baseline-OL value.

Entries of the open-label treatment phase will be added to the subject data listings, which have been prepared for the double-blind treatment phase. An additional flag will be added to indicate the entries of the open-label treatment phase. Updated data and additional entries of the double-blind treatment phase, other than new information on AEs, will need to be investigated.

To assess the safety and tolerability of the HMTM treatment given for up to 104 weeks, exposure, compliance, AEs, and laboratory data will be analyzed including data from the double-blind and open-label treatment phases. For subjects originally randomized to control, data gathered during the double-blind treatment phase will be excluded from this analysis, unless it is needed for the determination of a Baseline. These analyses will be performed based on the Safety-HMTM population (see Section 3.1.3).

#### 6.13.1. Extent of Drug Exposure and Compliance

The planned number of tablets taken by the subject each day for 52 weeks is four (2 tablets twice per day), with each tablet containing 4 mg of HMTM.

Based on the Safety-OL population, the following information will be summarized descriptively by treatment history and pooled treatment histories for the open-label treatment phase:

- Total duration of exposure (in weeks): (last dose date – first dose date + 1)/7
- Total duration of treatment (in weeks), which excludes days in which dose was interrupted
- Mean daily dose: Total of administered dose during the duration of exposure, relative to the total duration of exposure
- Total subject-years of exposure: sum of total exposure in years

$$\frac{1}{365.25} \sum_{\text{subjects}} \frac{\# \text{tablets taken}}{\# \text{tablets planned}} * \text{total duration of exposure (days)}$$

- Compliance: # Tablets taken / # tablets planned during the open-label treatment phase (or until early study drug termination), respectively. Including frequency and percentage of subjects with <80% and >120% compliance. The compliance values will be re-calculated and are not taken from the eCRF.
- Frequency and percentage of subjects with dose interruptions

Sponsor:	TauRx Therapeutics Ltd.		
Protocol:	TRx-237-039		
Document Version No.:	3.0	Document Date:	07-JUN-2023

---

- Frequency and percentage of subjects in the duration of exposure categories, based on total duration of exposure, including interruption days. The exposure categories can be taken from Section 5.12.1 (as done for the double-blind treatment phase analysis).

This summary will be also prepared including the combined treatment information from the double-blind and open-label treatment phases based on the Safety population, and for the HMTM treatment information from the double-blind and open-label treatment phases based on the Safety-HMTM population (see Section 3.1.3), which means that control treatment information during the double-blind treatment phase will be excluded from the analysis of the HMTM treatment information. The following exposure categories (in days) will be added for this analysis: 366-457, 458-548, 549-639, 640-730, and >730. For the summary of the combined treatment information, the treatment groups will distinguish between subjects who received no open-label treatment and subjects who did receive at least one dose of open-label treatment (e.g., MTC 8 mg/week, MTC 8 mg/week -> HMTM 16 mg).

For additional more general information regarding exposure and compliance, please see Section 5.12.1.

#### 6.13.2. Adverse Events

Adverse events (AEs) will be coded using the MedDRA version 20.1 and are displayed in tables and listings using SOC and Preferred Term (PT).

TEAEs during the open-label treatment phase are defined as AEs with:

- Onset after first dose of study drug of the open-label treatment phase or
- Worsen in intensity after first dose of study drug of the open-label treatment phase or
- Worsen in treatment relationship after first dose of study drug of the open-label treatment phase.

The total number of subjects and the numbers stratified by MedDRA SOC and PT, along with the corresponding percentage, will be derived and summarized by the original randomized treatment group from the double-blind treatment phase (MTC 8 mg/week, HMTM 8 mg/day, HMTM 16 mg/day), the pooled HMTM group (HMTM 8 mg/day + HMTM 16 mg/day), and overall, for the following events:

- Any TEAE
- Any TEAE with an onset on the first day of the open-label treatment phase after the first dose of the open-label treatment phase, complemented by a subject data listing
- Any TEAE (categorized by severity)
- Any TEAEs assessed by the Investigator as related to treatment (i.e., related or possibly related)
- Any TEAEs severe in intensity and assessed by the Investigator as related to treatment (as defined above)

Sponsor:	TauRx Therapeutics Ltd.		
Protocol:	TRx-237-039		
Document Version No.:	3.0	Document Date:	07-JUN-2023

---

- Any TEAE that resulted in interruption or discontinuation of study drug (presented separately and combined)
- Any serious adverse event (SAE)
- Any serious adverse reaction (SAR), which are the SAEs judged to be possibly related or related to the study drug by the Investigator
- Malignancies other than non-melanoma skin cancers
- *TauRx AE Groupings:* Subsets of TEAEs (defined by PT), summarized per grouping and sub-grouping (see Section 5.12.2).
- The protocol-specified AEs of special interest (AESI), which are hemolytic anemia and lens discoloration. A list of all identified events will be provided to the Statistical Programming team.

In addition, separate summaries of AEs by MedDRA SOC and PT will be provided for:

- Post-treatment TEAEs (after the open-label treatment phase)

For TOTOS subjects from the double-blind treatment phase, which continued off-treatment during the open-label treatment phase, a sub-population of the ITT-OL population – which are not included in the Safety-OL population, the following table and listing will be prepared:

- Any TEAE
- Subject data listing, which presents additional SAE information

### **HMTM Treatment Phase**

For the Safety-HMTM population (see Section 3.1.3), AEs of/ during the HMTM treatment will be analyzed. This means, that for subjects originally randomized to control, events of/ during the double-blind treatment phase (before the first dose of HMTM treatment during the open-label treatment phase) are excluded from this analysis.

The total number of subjects and the numbers stratified by MedDRA SOC and PT, along with the corresponding percentage, will be derived and summarized by the original randomized treatment group from the double-blind treatment phase (MTC 8 mg/week, HMTM 8 mg/day, HMTM 16 mg/day), the pooled HMTM group (HMTM 8 mg/day + HMTM 16 mg/day), and overall, for the following events:

- Any TEAE
- Any TEAE (categorized by severity)
- Any TEAEs assessed by the Investigator as related to treatment (i.e., related or possibly related)

Sponsor:	TauRx Therapeutics Ltd.		
Protocol:	TRx-237-039		
Document Version No.:	3.0	Document Date:	07-JUN-2023

- Any TEAEs severe in intensity and assessed by the Investigator as related to treatment (as defined above)
- Any TEAE that resulted in interruption or discontinuation of study drug (presented separately and combined)
- Any serious adverse event (SAE)
- Any serious adverse reaction (SAR), which are the SAEs judged to be possibly related or related to the study drug by the Investigator
- Malignancies other than non-melanoma skin cancers

For additional more general information regarding AEs, please see Section 5.12.2.

#### 6.13.3. Laboratory Data

Based on the (double-blind treatment phase) Safety population, the Baseline value, the actual value and change from Baseline for the Week 13, Week 26, Week 39, Week 52, Week 78, and Week 104 visits will be summarized by treatment group for the clinical laboratory parameters hemoglobin (separately for males and females), neutrophils, ALT, and AST; restricted to subjects with at least one post-Baseline value. Line graphs (showing the mean and standard error) of the observed data from Baseline to Week 104 will be presented for those parameters as well. The treatment groups will distinguish between subjects who received no open-label treatment and subjects who did receive at least one dose of open-label treatment (e.g., MTC 8 mg/week, MTC 8 mg/week -> HMTM 16 mg).

The Baseline-OL value is defined as the last non-missing value prior to the first dose of the open-label treatment phase study drug. Laboratory tests obtained on the date of the first dose will be assigned to pre-treatment; the relative times of blood sampling and dosing will be checked programmatically to confirm this assumption; if this is not true, a prior value will be used.

The Baseline-OL value, the actual value and change from Baseline-OL for the Week 56, Week 78, Week 104 visits, and for the last available on-treatment value will be summarized by treatment history for each clinical laboratory parameter, including hematology, and blood chemistry; restricted to subjects with at least one post-Baseline-OL value. For the hematology parameters hemoglobin and hematocrit, this descriptive analysis will be prepared separately for males and females.

Visit windows are used when results are presented by target visit (see Table 5 and Table 9). For each parameter, if a subject has multiple values within a visit window, the “worst” value will be used for that visit window summary (see Appendix 12.3).

Shift tables will be provided showing the change from Baseline-OL relative to the reference range. Missing categories will be included in the shift tables.

Box-and-whisker plots and line graphs (showing the mean and standard error) of the observed data from Baseline-OL to Week 104 (excluding visit Week 56) will be presented for the selected parameters

Sponsor:	TauRx Therapeutics Ltd.		
Protocol:	TRx-237-039		
Document Version No.:	3.0	Document Date:	07-JUN-2023

as described in Section 5.12.3. In addition to the original randomized treatment groups from the double-blind treatment phase, the figures will present the HMTM Pooled group results as well. The treatment group labels will be as described in Section 6.3.

Analogously to the double-blind treatment phase analysis, a summary will present two categories of PCS values:

- Subjects with any post-Baseline-OL PCS – the unique number of people who meet the criterion (regardless of whether or not they met it at Baseline-OL)
- Subjects with any post-Baseline-OL PCS Worsening
  - o Subjects who do not meet PCS criteria at Baseline-OL but do post-Baseline-OL or
  - o Subjects who already met the PCS criterion at Baseline-OL and in whom the post-Baseline-OL value is worse than it was at Baseline-OL.

When the PCS values are summarized, assessments after the first dose of the open-label treatment phase, that have been assigned to Week 52 by using the visit windowing (see Section 6.6), will be analyzed as Week 56 values.

The separate subject data listings with treatment-emergent PCS values will be created analogously to the double-blind treatment phase analysis, presenting the Baseline-OL and post-Baseline-OL PCS values.

### **HMTM Treatment Phase**

Since the scheduled study visits in the open-label treatment phase are planned every 26 weeks and not every 13 weeks as in the double-blind treatment phase, the analysis of the HMTM treatment phase will be divided into 26-week intervals. Visit windowing will be performed for the laboratory data based on the (double-blind treatment phase) study day for the early starters and based on the open-label treatment phase study day for the late starters. The following visit windows will be used:  $\leq 1$  (pre-dose) (Baseline-HMTM), 1 (post-dose) to 273 (Week 26, [day 183]), 274 to 456 (Week 52, [365]), 457 to 638 (Week 78, [548]), and  $\geq 639$  (Week 104, [730]), with the Baseline-HMTM value being defined as the last non-missing value prior to the first dose of HMTM treatment. If a subject has multiple values for a parameter within a visit window the rule from Section 5.5 will be used. For the subjects originally randomized to control, the values of the visits at Week 78 and 104 will be analyzed as Week 26 and Week 52 due to the delayed start of the HMTM treatment.

The following analysis will be performed based on the Safety-HMTM population (see Section 3.1.3).

The actual value and change from Baseline-HMTM for the Week 26, Week 52, Week 78, and Week 104 visits, and the last available on-treatment value, will be summarized by treatment history and overall, for each clinical laboratory parameter, including hematology, and blood chemistry; restricted to

Sponsor:	TauRx Therapeutics Ltd.		
Protocol:	TRx-237-039		
Document Version No.:	3.0	Document Date:	07-JUN-2023

---

subjects with at least one post-Baseline-HMTM value. For the hematology parameters hemoglobin and hematocrit, this descriptive analysis will be prepared separately for males and females.

Line graphs (showing the mean and standard error) of the observed data from Baseline-HMTM to Week 104 will be presented for selected parameters as described in Section 5.12.3. The treatment groups will be presented as described earlier in this section for the separate open-label treatment phase.

For additional more general information regarding laboratory analysis, please see Section 5.12.3.

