### 2.9.3. Safety Variables

Safety assessments performed during the study include the following:

- **Blood pressure** and **pulse** measured at Screening, Baseline pre-dose and approximately 2 hours post-dose, 4, 13, 26, 39, 52, 78, and 104 weeks, or early termination
- **Weight** measured at Screening, 4, 13, 26, 39, 52, 78, and 104 weeks, or early termination
- **Standard clinical laboratory** testing, including **hematology** and **blood (serum) chemistry**, performed at Screening, 4, 13, 26, 39, 52, 78, and 104 weeks, or early termination  
TSH, vitamin B12, folate, haptoglobin, and G6PD measured at Screening; a thyroid panel may be obtained in response to an elevated TSH. Additional testing as needed in response to an AE.
- Blood sample for a **serum pregnancy test** at Screening, 4, 13, 26, 39, 52, 78, and 104 weeks, or early termination, and up to 3 months after last dose of study drug; in women of childbearing potential, such women should be encouraged to return to the clinic or request serum pregnancy testing in the event of a delayed menstrual period to rule out possible pregnancy.
- **Targeted physical and neurological examinations** performed pre-dose and approximately 3 hours after administration of the first dose of study drug (Baseline). Thereafter, performed at 4, 13, 26, 39, 52, 78, and 104 weeks, or early termination. At a minimum, targeted examinations should include heart and lung auscultation and brief neurological assessment guided by any reported signs/symptoms/AEs (e.g., evaluating subjects for potential serotonin toxicity).
- **Ophthalmological examination** of subjects with history of lens implants performed prior to the first dose of study drug and at Week 52 and Week 104, to assess whether the lens has been discolored during the trial.
- Recording of **medications** administered within the last 90 days before Screening. Except for anti-dementia medications, where lifetime use (as far as possible) is to be recorded. Changes in concomitant medications and any new medications will be recorded at all subsequent visits, including the telephone contact.
- **AEs** recorded from the time the informed consent was signed throughout the study and, if pertinent, until resolution of the event. AEs with an onset after the first dose of study drug, or that worsen in intensity or treatment relationship after the first dose will be considered treatment-emergent adverse events (TEAE).

Sponsor:	TauRx Therapeutics Ltd.		

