### 5.5. Visit Windows

Since data might be documented under a wrong label (as a wrong visit) within the EDC system, all data will be (re-)assigned to a visit according to the column *Intervals for analysis* in Table 5.

Furthermore, if a subject has multiple values for a parameter within a visit window, the “worst” value will be used for that visit window summary (see Appendix 12.3), for efficacy endpoints the closest to the scheduled visit will be used (if two have the same distance from the scheduled visit the later one will be used, and if two have the same day, the Sponsor will provide a file, which identifies the value to be used in the analysis). For the double-blind treatment phase, priority at Week 52 is given to assessments that took place before initiation of the open-label treatment in case there are multiple values for them within the visit window.

Sponsor:	TauRx Therapeutics Ltd.		
Protocol:	TRx-237-039		
Document Version No.:	3.0	Document Date:	07-JUN-2023

As an exception, for the analysis of the double-blind treatment phase, a delayed Week 52 F-FDG-PET or MRI assessment will be included in the double-blind treatment phase even if it has been done within 14 days after first dose of the open-label treatment phase drug. In addition, the eye exam is eligible for the double-blind treatment phase, if it was performed until the end of the Week 52 protocol-specified visit window. For all other efficacy endpoints and safety information only assessments before the first dose of the open-label treatment phase or if assessments were done on the same day of the first open-label phase treatment are eligible for analysis of double-blind treatment phase data.

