#### 5.12.2. Adverse Events

Adverse events (AEs) will be coded using the MedDRA version 20.1 and are displayed in tables and listings using SOC and PT.

Treatment emergent AEs (TEAE) are defined as AEs with:

- Onset after first dose of study drug or
- Worsen in intensity after first dose of study drug or
- Worsen in treatment relationship after first dose of study drug

Based on the Safety population, a time-to-event analysis (event: any TEAE) will be performed using the model as described in Section 5.9.5). The time-to-first TEAE will be calculated as date of onset – date of first dose + 1, and subjects with no TEAE will be censored at the time of study discontinuation.

AEs are summarized by subject incidence rates, therefore, in any tabulation, a subject contributes only once to the count for a given AE (SOC or PT, most related occurrence, or most intense occurrence) regardless the number of episodes.

The total number of subjects and the numbers stratified by MedDRA SOC and PT, along with the corresponding percentage, with the following AE will be derived and summarized by treatment group and overall:

Sponsor:	TauRx Therapeutics Ltd.		
Protocol:	TRx-237-039		
Document Version No.:	3.0	Document Date:	07-JUN-2023

- Any TEAE (separate columns for true placebo and MTC)
- Any TEAE with an onset of Day 1 (separate columns for true placebo and MTC), complemented by a subject data listing
- Any TEAE (categorized by severity, and separate columns for true placebo and MTC), repeated for the Safetyv5 population.
- Any TEAE (categorized by severity) which occurred within two weeks after any COVID-19 vaccination (separate columns for true placebo and MTC)
- Any TEAEs assessed by the Investigator as related to treatment (i.e., related or possibly related) (separate columns for true placebo and MTC)
- Any TEAEs severe in intensity and assessed by the Investigator as related to treatment (as defined above) (separate columns for true placebo and MTC)
- Any TEAE that resulted in interruption or discontinuation of study drug (presented separately and combined) (separate columns for true placebo and MTC)
- Any SAE (separate columns for true placebo and MTC)
- Any serious adverse reaction (SAR), which are the SAEs judged to be possibly related or related to the study drug by the Investigator (separate columns for true placebo and MTC)
- Malignancies other than non-melanoma skin cancers (separate columns for true placebo and MTC)

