### 12.3. Rules for Determining “Worst” Value

#### 12.3.1. Clinical Laboratory Parameters

Rule	Parameters
	Hematology: eosinophils, basophils, monocytes, reticulocytes
Highest value	Blood chemistry: ALT, AST, ALK-P, bicarbonate, creatinine, direct/indirect/total bilirubin, BUN, LDH, TSH, GGT, urea nitrogen
	Hematology: neutrophils, RBC count, HCT, hemoglobin, platelets
Lowest value	Blood chemistry: albumin, creatinine clearance, total protein, Triiodothyronine, Thyroxine, folate, and B12
	Hematology: WBC count, lymphocytes, MCV, MCH, MCHC
Farthest from normal range midpoint	Blood chemistry: glucose (random), sodium, potassium, phosphorus, calcium, chloride

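### The HMTM-phase lab and AE summaries put early and late starters side by side on unequal sampling and follow-up, so differences can appear with no drug effect

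*SAP*

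**What the plan says.** **Laboratory data.** SAP 6.13.3 (HMTM Treatment Phase) divides time on HMTM into 26-week intervals because the open-label phase is sampled less often than the double-blind phase. The first two post-dose windows are "1 (post-dose) to 273 (Week 26, [day 183]), 274 to 456 (Week 52, [365"]). Days are counted from the first double-blind dose in early starters and from the first open-label dose in late starters. For the original control arm, "the values of the visits at Week 78 and 104 will be analyzed as Week 26 and Week 52 due to the delayed start". For several values in one window the section states: "If a subject has multiple values for a parameter within a visit window the rule from Section 5.5 will be used". The Section 5.5 rule is: "if a subject has multiple values for a parameter within a visit window, the “worst” value will be used". The closest-to-schedule rule in that section is reserved for efficacy. Appendix 12.3.1 puts "Hematology: neutrophils, RBC count, HCT, hemoglobin, platelets" under lowest value and ALT, AST, bilirubin and reticulocytes under highest. Actual values and changes are then tabulated by treatment history and overall, with line graphs for selected parameters.

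**Adverse events.** SAP 6.13.2 (HMTM Treatment Phase) tabulates numbers and percentages of subjects by original arm, pooled HMTM arms and overall. Events in the control arm before the first HMTM dose are left out. The counting rule comes from SAP 5.12.2: "AEs are summarized by subject incidence rates, therefore, in any tabulation, a subject contributes only once to the count for a given AE". No exposure-adjusted rate or common time cut is specified for these tables.

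**The concern.** The minimum or maximum of several noisy values is systematically more extreme than a single value. If one column reports the worst of three or four samples and the next column reports one, the first looks worse even when the drug does nothing. Because the number of samples per window also falls over time in early starters, their own curve would worsen at Week 26 and then recover, which resembles a transient effect of first exposure. Late starters outside the UK could not show it.

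For AEs, a once-per-subject percentage rises with time under observation. Early starters would appear at higher risk simply because they were followed for longer, and the overall column would mix two follow-up lengths without representing either. These tables are the SAP's answer to the objective on safety over up to 104 weeks, so they are likely to be read across columns.

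**Working it through.** The documents give no figure for these tables, so there is none to reproduce.

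**1. Lab values per window.** SAP 2.9.3 has standard laboratory tests "performed at Screening, 4, 13, 26, 39, 52, 78, and 104 weeks, or early termination".
- *Early starters, Week 26 window:* Weeks 4, 13 and 26 always fall inside. The Week 39 visit may be on Days 260 to 288 (SAP Table 5); on Days 260 to 273 it adds a fourth value. If visits are spread evenly over the 29 days, that happens in 14/29 = 48% of cases, so the mean count is 3.48.
- *Early starters, Week 52 window:* Week 52, plus Week 39 in the other 52%, so the mean count is 1.52. At UK sites the on-site Week 56 sample (SAP Table 3) can make it three.
- *Early starters, Weeks 78 and 104:* one value each.
- *Late starters:* one value in each of their two windows. At UK sites Week 56 may give a second in the first window; the SAP does not say how that value is used.

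**2. Expected worst value with no drug effect**, in within-subject SD units. The expected minimum of k independent normal deviates is 0 (k=1), -0.56 (k=2), -0.85 (k=3) and -1.03 (k=4). With equal correlation r between deviations, multiply by √(1-r). At r = 0.5, k=3 gives -0.85 × 0.71 = -0.60 and k=4 gives -0.73.
- Early starters with Week 39 on Day 274 or later: -0.85, -0.56, 0, 0 at Weeks 26, 52, 78, 104.
- Early starters with Week 39 by Day 273: -1.03, 0, 0, 0.
- Averaged at Week 26: 0.52 × (-0.85) + 0.48 × (-1.03) = about -0.93. At Week 52: 0.52 × (-0.56) = about -0.29.
- Late starters: 0 outside the UK; up to -0.56 in the first window in the UK.

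For hemoglobin, assuming a within-subject SD of 3 to 8 g/L, the Week 26 artifact is 2.5 to 6.8 g/L (three values) or 3.1 to 8.2 g/L (four). Parameters whose worst value is the highest show a rise of the same size in SD units. With 250 early and 155 late starters (200 × 0.75 to 0.80 gives 150 to 160) and independent values, the difference is about 6 to 7.5 standard errors.

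**3. AE incidence with equal constant hazards.** Dropout is the plan's own: 20 to 25% in the double-blind year (SAP 5.3) and 10% in the open-label year (SAP 6.4), spread evenly within each.
- Mean HMTM exposure, early: 52 × (1 - 0.20/2) + 0.80 × 52 × (1 - 0.10/2) = 86.3 weeks at 20% dropout, about 82.5 at 25%. Late: 52 × 0.95 = 49.4 weeks.
- Let p be the 52-week incidence and F(t) = 1 - (1-p)^(t/52). Early = d1 × mean F over 0-52 + (1-d1) × [d2 × mean F over 52-104 + (1-d2) × F(104)]. Late = d2 × mean F over 0-52 + (1-d2) × p.
- For p = 13% (the anemia-term figure in Protocol 8.1.3.4, used here as an assumed 52-week level), d1 = 0.20 and d2 = 0.10: early = 0.20 × 0.0665 + 0.80 × (0.10 × 0.1879 + 0.90 × 0.2431) = 20.3%; late = 0.10 × 0.0665 + 0.90 × 0.13 = 12.4%.

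| p | Early (20% / 25% dropout) | Late | Ratio |
|---|---|---|---|
| 5% | 8.1% / 7.8% | 4.75% | 1.71 / 1.63 |
| 13% | 20.3% / 19.5% | 12.4% | 1.645 / 1.575 |
| 21% | 31.6% / 30.3% | 20.0% | 1.58 / 1.52 |
| 50% | 64.7% / 62.4% | 47.8% | 1.35 / 1.31 |

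**4. After the change.** One value per window in both groups gives an expected lab difference of 0. Limiting AEs to the first 52 weeks on HMTM gives 11.7% or 11.4% against 12.4% for p = 13%, a ratio of 0.92 to 0.95; what remains is the heavier first-year dropout. First events per subject-year at risk give a ratio of 1.0. With total exposure as denominator, p = 13% gives (20.34/86.3)/(12.37/49.4) = 0.94, but p = 50% gives (64.69/86.3)/(47.79/49.4) = 0.77, so for common events time should stop at the first event.

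**The case against.** The strongest reply is that these are descriptive tables and that better-matched views are planned elsewhere. SAP 6.13 gives their purpose as describing HMTM safety over up to 104 weeks, and SAP 5.12.2 rules out formal testing of AE incidence. SAP 6.13.3 also summarizes hemoglobin, neutrophils, ALT and AST by study visit across both phases in narrower windows, with about one scheduled value each. The double-blind tables show early starters against a randomized control on the same sampling schedule. First-year AEs on HMTM can be pieced together from the double-blind table (early starters) and the open-label table (late starters). Subject-years are reported for the Safety-HMTM population. Taking the worst value is a uniform safety convention that errs toward signalling harm.

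All of that stands and lowers the weight of the point. It does not repair the tables themselves. The by-visit view across both phases covers four parameters, while the HMTM-phase tables cover every hematology and chemistry parameter and their graphs add reticulocytes, platelets, GGT and total bilirubin. The AE tables still carry a crude percentage and a mixed overall column. The convention is conservative in one column only.

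A reader might go further and infer that the plan would generate a false hemolytic anemia signal. The documents do not support that: this event of special interest is tabulated from a list of identified events, not from mean hemoglobin, and the HMTM-phase AE list has no row for it. Nor do they support saying that late starters can show no artifact at all, since UK late starters may have two values.

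**Conclusion.** The point holds as a fault in descriptive safety summaries. Followed as written, the SAP gives early starters an artifactual Week 26 lab worsening of about 0.85 to 1.03 within-subject SD under independence, or about 0.6 to 0.7 SD at correlation 0.5. It is smaller at Week 52 and absent at Weeks 78 and 104. The direction follows from the windows and the rule; the size in g/L depends on an assumed SD. For AEs, equal hazards give a crude ratio of about 1.3 to 1.7, assuming a constant hazard, 52-week incidence of 5 to 50% and the plan's dropout. The 104 and 52 weeks are maxima; expected exposure is about 82 to 86 against 49 weeks.

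It would be wrong to read this as a biased hypothesis test or as a planned randomized comparison. The Safety-HMTM population keeps HMTM-arm dropouts but excludes controls who never entered the open-label phase, so late starters remain a selected group even after the change.

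**What to change.** **SAP 6.13.3, HMTM phase.** For tables of actual value and change, and for line graphs, use the value closest to Day 183, 365, 548 or 730, the principle that Section 5.5 already applies to efficacy: "value will be used for that visit window summary (see Appendix 12.3), for efficacy endpoints the closest to the scheduled visit will be used". State how the UK Week 56 value is handled. Add a separate summary of the worst value after Baseline-HMTM, because this section plans no table of potentially clinically significant values that would otherwise keep it.

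**SAP 6.13.2, HMTM phase.** Add incidence per 100 subject-years on HMTM, using the exposure data already assembled for Safety-HMTM. The SAP's subject-year total is scaled by tablets taken and does not stop at the first event, so define time at risk explicitly. Add one table of the first 52 weeks on HMTM for every group, and use it for reading early against late starters.

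**Cost.** SAP wording and minor programming; no new data. The mean tables would no longer carry the worst intermediate value, which moves to the added summary.
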